8.0 EVALUATIONS/MATERIAL AND DATA TO BE ACCESSIONED

8.1 Required Clinical, Laboratory and Disease Evaluation

All clinical and laboratory studies to determine eligibility must be performed within 7 days prior to enrollment unless otherwise indicated. Laboratory values used to assess eligibility (see [Section 4.0](#)) must be no older than seven (7) days at the start of therapy. Laboratory tests need **not** be repeated if therapy starts **within** seven (7) days of obtaining labs to assess eligibility. If a post-enrollment lab value is outside the limits of eligibility, or laboratory values are older than 7 days, then the following laboratory evaluations must be re-checked within 48 hours prior to initiating therapy: CBC with differential, bilirubin, ALT (SGPT) and serum creatinine. If the recheck is outside the limits of eligibility, the patient may not receive protocol therapy and will be considered off protocol therapy. Imaging studies must be obtained within 14 days prior to start of protocol therapy (repeat the tumor imaging if necessary).

STUDIES TO BE OBTAINED	Pre-Study	During Cycle 1	Prior to Subsequent Cycles[^]
History	X	Weekly	X
Physical Exam with vital signs	X	Weekly	X
Height, weight, BSA	X		X
Performance Status	X		
CBC, differential, platelets	X	Twice Weekly	Weekly ³
Pharmacokinetics ¹	X	X	X
Urinalysis	X		
Electrolytes including Ca ²⁺ , PO ₄ ³⁻ , Mg ²⁺ ; glucose	X	Weekly	X
Creatinine, ALT, bilirubin	X	Weekly	X
Albumin	X		X
Tumor Disease Evaluation	X	End of Cycle 1	Every other cycle x 2 then q 3 cycles ⁴
Pharmacodynamics Studies (H3 and H4 Histone Acetylation in PBMCs) ⁶	X	X ⁷	
Pregnancy Test ²	X		
Patient Diary ⁵		Weekly	X

[^] Studies may be obtained within 72 hours prior to the start of the subsequent cycle.

¹ See [Section 8.3](#) for timing of PK studies.

² Women of childbearing potential require a negative pregnancy test prior to starting treatment; sexually active patients must use an acceptable method of birth control. Abstinence is an acceptable method of birth control. Patients of reproductive potential must use secure methods of contraception during treatment and for 3 additional months after the end of treatment. Those who become pregnant while on treatment with entinostat must discontinue immediately and consult their treating physician.

³ If patients develop Grade 4 neutropenia or Grade 4 thrombocytopenia then CBCs should be checked every 3 to 4 days until recovery to Grade 3.

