12.4.5 Overall Best Response Assessment

Each patient will be classified according to his “best response” for the purposes of analysis of treatment effect. Best response is determined from the sequence of the overall response assessments as described in Table 3 in [Section 12.6](#).

12.5 **Response Criteria for Patients with CNS Tumors**

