12.6 Best Response

12.6.1 Evaluation of Best Overall Response

The best overall response is the best response recorded from the start of the treatment until disease progression/recurrence (taking as reference for progressive disease the smallest measurements recorded since the treatment started). The patient's best response assignment will depend on the achievement of both measurement and confirmation criteria.

Table 3. Sequences of overall response assessments with corresponding best response.

1st Assessment	2nd Assessment	Best Response
Progression		Progressive disease
Stable, PR, CR	Progression	Progressive disease
Stable	Stable	Stable
Stable	PR, CR	Stable
Stable	Not done	Not RECIST classifiable
PR	PR	PR
PR	CR	PR
PR, CR	Not done	Not RECIST classifiable
CR	CR	CR

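### Best-response Table 3 contradicts the definition above it and Table 1, and leaves three response sequences without a category

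*Combined protocol and SAP*

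**What the plan says.** Section 12.6.1 opens with a whole-course definition: "The best overall response is the best response recorded from the start of the treatment until disease progression/recurrence". It then adds a condition: "The patient's best response assignment will depend on the achievement of both measurement and confirmation criteria".

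The table under it is headed "Table 3. Sequences of overall response assessments with corresponding best response", but its only inputs are a 1st and a 2nd assessment. Three rows matter here: "Stable PR, CR Stable", "Stable, PR, CR Progression Progressive disease" and "PR, CR Not done Not RECIST classifiable".

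Sections 12.2.6, 12.3.6 and 12.5.7 send best response to Section 12.6 as a whole. Section 12.4.5, for MIBG-positive neuroblastoma, names the table itself: "Best response is determined from the sequence of the overall response assessments as described in Table 3".

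Section 8.1 schedules tumor evaluation at the end of Cycle 1 and then "Every other cycle x 2 then q 3 cycles". Its footnote 4 and Section 12.2 call for a further scan in the next consecutive cycle after a first PR or CR.

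Table 1 in Section 12.2.5 gives its own conditions for best overall response. CR and PR need confirmation at 28 days or more. SD needs one documentation at 28 days or more from baseline. PD applies only if there was no earlier SD, PR or CR.

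**The concern.** The section gives two rules for one quantity. The text looks across all scans up to progression; the table looks at two. A response first seen at the second scan can be confirmed only at the third, and the table cannot use the third. Someone coding from the table and someone coding from the paragraph would put the same patient in different categories.

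The table is also incomplete, and two of its rows disagree with Table 1. Section 12.6.2 adds to the confusion: response duration starts when PR or CR measurements are first met, so a patient could have a response duration and a best response of Stable.

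At stake is the reporting of secondary aim 1.2.1. With few patients and no fixed rule, the choice between the readings would fall to whoever classifies the patients, possibly after the responses are known.

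**Working it through.** The plan states no figure to reproduce. The check sets the rules side by side and counts cases. Sequences are written in scan order, so SD-PR-PR means SD, then PR, then PR.

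**Step 1. Pairs in Table 3.** A first assessment of SD, PR or CR and a second of CR, PR, SD, PD or not done gives 3 × 5 = 15 pairs.

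| First | then CR | then PR | then SD | then PD | then not done |
|---|---|---|---|---|---|
| SD | Stable | Stable | Stable | PD | not classifiable |
| PR | PR | PR | no row | PD | not classifiable |
| CR | CR | no row | no row | PD | not classifiable |

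Rows exist for 5 + 4 + 3 = 12 pairs, and 15 − 12 = 3 have none. The gaps can occur. PR-SD needs only a partial regrowth that stays below the PD thresholds of Section 12.2.4.1 (20% and 5 mm above the smallest sum). CR-PR can arise under Table 1 when non-target lesions are not evaluated at the later scan, or under the CNS table when markers become abnormal. CR-SD should be rarer, because most regrowth after a CR would meet the PD criteria.

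**Step 2. A late responder on the schedule.** Counting every other cycle from Cycle 1, the scans are at the end of Cycle 1 (SD), the end of Cycle 3 (PR) and, as the required confirmation, the end of Cycle 4 (PR). The definition gives PR. Table 3 stops after the second scan and gives Stable.

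**Step 3. All three-scan sequences that do not start with PD.** Assumptions: PD ends the sequence; no scan is missed; PR or CR counts when that category or better is met at two consecutive scans; otherwise a patient with a non-PD scan is SD, the 28-day condition being met. The confirmation reading is an assumption, because the text does not spell it out.

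Each of 3 first results is followed either by PD (1 way) or by 3 non-PD results, each with 4 possible third results: 3 × (1 + 3 × 4) = 39 sequences.

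- No row in Table 3: 3 missing pairs × 4 third results = 12.
- Different category: 8. SD-PR-PR, SD-PR-CR and SD-CR-PR are Stable against PR. SD-CR-CR is Stable against CR. PR-CR-CR is PR against CR. SD-PD, PR-PD and CR-PD are PD against SD. In all eight, Table 3 gives the less favorable category.
- Same category: 39 − 12 − 8 = 19.

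Under the text, 20 of the 39 hold a confirmed PR or CR. Table 3 gives PR or CR for 12 of them, Stable for 4, and no row for 4 (those starting CR-PR): 12 + 4 + 4 = 20. These are counts of possible sequences, not of expected patients.

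**Step 4. Table 3 against Table 1.**

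| Situation | Table 3 | Table 1 |
|---|---|---|
| SD, PR or CR, then progression | PD | PD excluded, since an earlier SD, PR or CR exists |
| SD, then not done | not classifiable | SD, if documented once at 28 days or more from baseline |

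This reads Table 1's PD condition as covering all its PD rows.

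**The case against.** The strongest reply is that the opening sentence of 12.6.1 controls and that Table 3 is a confirmation rule for any consecutive pair. Much supports this. Three of the four disease sections refer to Section 12.6 and to a sequence of assessments. Table 1 does not tie confirmation to the first two scans. A confirmatory scan after any first PR or CR would have little purpose if a late response could not count.

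So a reader might infer that only responses already present after the four Cycle 1 doses can ever count. The documents do not support that as the plan's rule. It is the literal result of the table, and the definition above the table says otherwise.

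A reader might also infer that every unconfirmed response lacks a row. That is not so either: PR or CR then progression, and PR or CR then not done, each have one. The gap is limited to PR-SD, CR-SD and CR-PR.

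What remains is that nothing in the section says the table applies to each consecutive pair. The columns are labeled 1st and 2nd, and Section 12.4.5 makes the table the operative rule for MIBG disease. Even read pair by pair, SD-PR-PR yields Stable from one pair and PR from the next, with no rule for which prevails. The three gaps and both conflicts with Table 1 also remain.

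It is fair, too, that response is a secondary aim which Section 11.5 treats as descriptive and exploratory. No threshold, test or escalation decision uses best response.

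**Conclusion.** The point stands as an internal contradiction: Table 3 disagrees with the definition directly above it and with Table 1. Followed literally, it misclassifies confirmed late responses and late upgrades to CR, leaves 3 of 15 pairs unassigned, and conflicts with Table 1 on two further rows. It should be corrected before responses are classified.

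The effect is confined to secondary aim 1.2.1. DLT, MTD and sample size are unaffected.

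It cannot be sized as a response rate. A reader might divide one misclassified patient by 22 or 18 and quote 1/22 = 4.5% to 1/18 = 5.6%. But in Section 11.1, 22 is the expected maximum enrollment, including a 20% inevaluable allowance, and 18 is that plan without the allowance (6 + 6 + 6). Section 12.2.1.1 restricts response evaluability mainly to patients with measurable baseline disease who received a cycle and were re-evaluated, and the documents give no number for them. Across the enrollment range in Section 11.1, 4 to 36, one patient would be 1/4 = 25% to 1/36 = 2.8%. Nothing in the documents predicts how many late responders there will be.

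The counts in Step 3 rest on the confirmation reading given there. The count of missing pairs and the conflicts with Table 1 do not.

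**What to change.** In Section 12.6.1:

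1. State that best response is the best category over the whole sequence up to progression. PR or CR counts when that category or better is met and is met again at the next assessment at least 28 days later, at whatever scan it first appears.
2. State that Table 3 is a rule for each consecutive pair and that the best pair prevails. SD-PR-PR then gives Stable and PR, hence PR; PR-CR-CR gives PR and CR, hence CR.
3. Add the missing rows: PR-SD and CR-SD as SD if the 28-day condition for SD in Table 1 is met, and CR-PR as PR unless the change meets the protocol's own PD criteria.
4. Reconcile two existing rows with Table 1. The row for SD, PR or CR then progression should not return PD where Table 1 excludes it. The row for Stable then not done should return SD where one documentation at 28 days or more exists.

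The cost is one paragraph, three new rows and two revised rows. No extra scans are needed, because the confirmatory scan is already required; its timing has only to respect the 28 days in Table 1. Dosing, DLT assessment and enrollment do not change.

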12.6.2 Duration of Response

Duration of overall response: The duration of overall response is measured from the time measurement criteria are met for CR or PR (whichever is first recorded) until the first date that recurrent or progressive disease is objectively documented (taking as reference for progressive disease the smallest measurements recorded since the treatment started).

The duration of overall CR is measured from the time measurement criteria are first met for CR until the first date that progressive disease is objectively documented.

Duration of stable disease: Stable disease is measured from the start of the treatment until the criteria for progression are met, taking as reference the smallest measurements recorded since the treatment started, including the baseline measurements.

13.0 ADVERSE EVENT REPORTING REQUIREMENTS

Adverse event data collection and reporting which are required as part of every clinical trial, are done to ensure the safety of patients enrolled in the studies as well as those who will enroll in future studies using similar agents. Adverse events are reported in a routine manner at scheduled times during a trial. (Please follow directions for routine reporting provided in the Case Report Forms for this protocol). Additionally, certain adverse events must be reported in an expedited manner to allow for optimal monitoring of patient safety and care. The following sections provide information about expedited reporting.

Reporting requirements may include the following considerations: 1) whether the patient has received an investigational or commercial agent; 2) whether the adverse event is considered serious; 3) the grade (severity); and 4) whether or not hospitalization or prolongation of hospitalization was associated with the event.

An investigational agent is a protocol drug administered under an Investigational New Drug Application (IND). In some instances, the investigational agent may be available commercially, but is actually being tested for indications not included in the approved package label.

Commercial agents are those agents not provided under an IND but obtained instead from a commercial source. The NCI, rather than a commercial distributor, may on some occasions distribute commercial agents for a trial.

13.1 Steps to Determine If an Adverse Event Is To Be Reported In an Expedited Manner

Step 1: Identify the type of adverse event using the NCI CTCAE version 5.0. All appropriate treatment areas should have access to a copy of the CTCAE version 5.0. A copy of the CTCAE version 5.0 can be downloaded from the CTEP website (http://ctep.cancer.gov/protocolDevelopment/electronic_applications/ctc.htm).

Step 2: Grade the adverse event using the NCI CTCAE.

Step 3: Review Table A in this section to determine if:

- the adverse event is considered serious;
- there are any protocol-specific requirements for expedited reporting of specific adverse events that require special monitoring; and/or

- there are any protocol-specific exceptions to the reporting requirements.

Note: This includes all events that occur within 30 days of the last dose of protocol treatment. Any event that occurs more than 30 days after the last dose of treatment and is attributed (possibly, probably, or definitely) to the agent(s) must also be reported according to the instructions in the table below. Attribution categories are as follows: Unrelated, Unlikely, Possible, Probable, and Definite.

Table A: Phase 1 and Early Phase 2 Studies: Expedited Reporting Requirements for Adverse Events that Occur on Studies under an IND/IDE within 30 Days of the Last Administration of the Investigational Agent/Intervention ^{1,2}

FDA REPORTING REQUIREMENTS FOR SERIOUS ADVERSE EVENTS (21 CFR Part 312) NOTE: Investigators MUST immediately report to the sponsor ANY Serious Adverse Events, whether or not they are considered related to the investigational agent(s)/intervention (21 CFR 312.64) An adverse event is considered serious if it results in ANY of the following outcomes:
 
 1) Death 2) A life-threatening adverse event 3) An adverse event that results in inpatient hospitalization or prolongation of existing hospitalization for \geq 24 hours 4) A persistent or significant incapacity or substantial disruption of the ability to conduct normal life functions 5) A congenital anomaly/birth defect. 6) Important Medical Events (IME) that may not result in death, be life threatening, or require hospitalization may be considered serious when, based upon medical judgment, they may jeopardize the patient or subject and may require medical or surgical intervention to prevent one of the outcomes listed in this definition. (FDA, 21 CFR 312.32; ICH E2A and ICH E6). 		

ALL SERIOUS adverse events that meet the above criteria MUST be immediately reported via CTEP-AERS within the timeframes detailed in the table below.
		
Hospitalization	Grade 1 and Grade 2 Timeframes	Grade 3-5 Timeframes
Resulting in Hospitalization \geq 24 hrs	7 Calendar Days	24-Hour 5 Calendar Days
Not resulting in Hospitalization \geq 24 hrs	Not required	

NOTE: Protocol specific exceptions to expedited reporting of serious adverse events are found in the Specific Protocol Exceptions to Expedited Reporting (SPEER) portion of the CAEPR. Expedited AE reporting timelines are defined as:
 
 ○ "24-Hour; 5 Calendar Days" - The AE must initially be reported via CTEP-AERS within 24 hours of learning of the AE, followed by a complete expedited report within 5 calendar days of the initial 24-hour report. ○ "7 Calendar Days" - A complete expedited report on the AE must be submitted within 7 calendar days of learning of the AE. 		

¹Serious adverse events that occur more than 30 days after the last administration of investigational agent/intervention and have an attribution of possible, probable, or definite require reporting as follows: Expedited 24-hour notification followed by complete report within 5 calendar days for:
 
 • All Grade 3, 4, and Grade 5 AEs 
Expedited 7 calendar day reports for:
		

- Grade 2 AEs resulting in hospitalization or prolongation of hospitalization

² For studies using PET or SPECT IND agents, the AE reporting period is limited to 10 radioactive half-lives, rounded UP to the nearest whole day, after the agent/intervention was last administered. Footnote "1" above applies after this reporting period.

Effective Date: May 5, 2011

- Any medical event equivalent to CTCAE grade 3, 4, or 5 that precipitates hospitalization (or prolongation of existing hospitalization) must be reported regardless of attribution and designation as expected or unexpected with the exception of any events identified as protocol-specific expedited adverse event reporting exclusions.
- Any event that results in persistent or significant disabilities/incapacities, congenital anomalies, or birth defects must be reported via CTEP-AERS if the event occurs following treatment with an agent under a CTEP IND.
- Use the NCI protocol number and the protocol-specific patient ID provided during trial registration on all reports.

Additional Instructions or Exceptions to CTEP-AERS Expedited Reporting Requirements for Phase 1 Trials Utilizing an Agent under a CTEP-IND or Non-CTEP IND:

- Any death that occurs more than 30 days after the last dose of treatment with an investigational agent which can be attributed (possibly, probably, or definitely) to the agent and is not clearly due to progressive disease must be reported via CTEP-AERS for an agent under a CTEP or non-CTEP IND agent per the timelines outlined in the table above.
- Myelosuppression, (Grade 1 through Grade 4 adverse events as defined in the table below), does not require expedited reporting, unless it is associated with hospitalization.

Category	Adverse Events
INVESTIGATIONS	Platelet count decreased
INVESTIGATIONS	White blood cell decreased
INVESTIGATIONS	Neutrophil count decreased
INVESTIGATIONS	Lymphocyte count decreased
BLOOD/LYMPHATICS DISORDERS	Anemia

- Grade 1 and 2 adverse events listed in the table below do **not** require expedited reporting via CTEP-AERS:

Category	Adverse Events
BLOOD AND LYMPHATIC SYSTEM DISORDERS	Febrile neutropenia
GASTROINTESTINAL DISORDERS	Flatulence
GENERAL DISORDERS AND ADMINISTRATION SITE CONDITIONS	Non-cardiac chest pain
INVESTIGATIONS	Alanine aminotransferase increased
	Aspartate aminotransferase increased
	Blood bilirubin increased
	Creatinine increased

	Weight loss
METABOLISM AND NUTRITION DISORDERS	Hypomagnesemia
MUSCULOSKELETAL AND CONNECTIVE TISSUE DISORDERS	Arthralgia
	Back pain
	Generalized muscle weakness
	Pain in extremity
RESPIRATORY, THORACIC AND MEDIASTINAL DISORDERS	Epistaxis

- See also the Specific Protocol Exceptions to Expedited Reporting (SPEER) in [Section 9.1.8](#) of the protocol. Additional protocol-specific exceptions to expedited reporting of serious adverse events are the toxicities in bold font listed under the drug information section of the protocol ([Section 9.1](#)).

As referenced in the CTEP Adverse Events Reporting Requirements, an AE that resolves and then recurs during a subsequent cycle does not require CTEP-AERS reporting unless (1) the Grade increases; or (2) hospitalization is associated with the recurring AE.

13.2 When to Report an Event in an Expedited Manner

- Some adverse events require notification **within 24 hours** (refer to Table A) to NCI via the web at <http://ctep.cancer.gov> (telephone CTEP at: **[contact]** within 24 hours of becoming aware of the event if the CTEP-AERS 24-Hour Notification web-based application is unavailable) and by telephone call to the Study Chair. Once internet connectivity is restored, a 24-hour notification phoned in must be entered electronically into CTEP-AERS by the original submitter at the site.
- When the adverse event requires expedited reporting, submit the report **within 5 or 7 calendar days** of learning of the event (refer to Table A).
- Expedited AE reporting for this study must only use CTEP-AERS (Adverse Event Expedited Reporting System), accessed via the CTEP home page at <https://eapps-ctep.nci.nih.gov/ctepaers>.

13.3 Expedited Reporting Methods

13.3.1 CTEP-AERS Reporting

To report adverse events in an expedited fashion use the NCI's Adverse Event Expedited Reporting System (CTEP-AERS) that can be found at <http://ctep.cancer.gov>.

A CTEP-AERS report must be submitted electronically via the CTEP-AERS Web-based application located at <https://eapps-ctep.nci.nih.gov/ctepaers>. If prompted to enter a sponsor email address, please type in: [contact].

Send supporting documentation to the NCI by fax ([contact]) and by email to the ADVL1513 COG Study Assigned Research Coordinator. **ALWAYS include the ticket number on all faxed and emailed documents.**

13.4 Definition of Onset and Resolution of Adverse Events

Note: These guidelines below are for reporting adverse events on the COG case report forms and do not alter the guidelines for CTEP-AERS reporting.

13.4.1 If an adverse event occurs more than once in a course (cycle) of therapy only the most severe grade of the event should be reported.

13.4.2 If an adverse event progresses through several grades during one course of therapy, only the most severe grade should be reported.

13.4.3 The duration of the AE is defined as the duration of the highest (most severe) grade of the Adverse Effects.

13.4.4 The resolution date of the AE is defined as the date at which the AE returns to baseline or less than or equal to Grade 1, whichever level is higher (note that the resolution date may therefore be different from the date at which the grade of the AE decreased from its highest grade). If the AE does not return to baseline the resolution date should be recorded as "ongoing."

13.4.5 An adverse event that persists from one course to another should only be reported once unless the grade becomes more severe in a subsequent course. An adverse event which resolves and then recurs during a different course, must be reported each course it recurs.

